Before finalising our interpretation on clinical relevance of our findings, we will assess the safety of the two treatment arms:

Table 3. Complications, adverse events, re-admissions to hospital

According to our own data on the safety of the ACDF procedure (overall complications rates < 10%), this analysis will likely not be powered to materially change our main conclusion, particularly with regards to the most feared complication (neck haematoma), which has a reported incidence of <1%.

Having said this, to be completely transparent and inclusive about the possible effect of adverse consequences on the clinical relevance (our interpretation) of the trial findings, we commit to assessing the overall rate (incidence) of safety concerns before final interpretation is made as follows:

If we detect > 10% difference in the overall incidence of serious adverse events between the two group (treatment strategies), we will add the following notion in our conclusion:

“However, there was a noteworthy imbalance in the incidence of safety concerns in the two treatment strategies (higher/lower rate in Group A) and this should be considered when interpreting the trial findings.”

As noted, the analysis on the downsides of the two treatments will not change our assessment on efficacy, rather modify our interpretation on the clinical relevance of the trial.

The sequence of events to take place in the upcoming “blinded data interpretation meeting” is outlined in the flow chart below:

1. Analysis on efficacy (primary, non-inferiority): Is outpatient care non-inferior to inpatient care after anterior cervical decompression and fusion?

Table 1. Baseline characteristics.

Table 2. Primary outcome (NDI) at the primary outcome assessment time point (6 months).

Figure 2. Scenario 1: Group A minus Group B.

Figure 3. Scenario 2: Group B minus Group A.

Initial interpretation on efficacy

2. Incidence of safety concerns: Imbalance?

Table 3. Complications, adverse events, re-admissions to hospital (with 30 days post-operatively), and reoperations.

NO

Initial interpretation on efficacy stands

YES

A notion on downsides to be added to the initial interpretation on efficacy

3. Unblinding

4. Unblinded interpretation on efficacy and clinical relevance

5. Final interpretation (signed by all involved)

1. Analysis on efficacy (primary, non-inferiority): Is outpatient care non-inferior to inpatient care after anterior cervical decompression and fusion?

[figure not shown]

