Based on the location of the whole CI in relation to Δ (non-inferiority margin), our initial interpretation on the non-inferiority of Outpatient care (vs. Inpatient care), is as follows:

Scenario 1 (Figure 2) [incorrect options to be removed]

Group A is [superior **A** / non-inferior **B** to **D** / inferior **H**] to Group B after anterior cervical decompression and fusion.

OR

Our results are inconclusive [**E** to **G**] regarding the non-inferiority of the two groups after anterior cervical decompression and fusion.

Scenario 2 (Figure 3) [incorrect options to be removed]

Group B is [superior **A** / non-inferior **B** to **D** / inferior **H**] to Group A after anterior cervical decompression and fusion.

OR

Our results are inconclusive [**E** to **G**] regarding the non-inferiority of the two groups after anterior cervical decompression and fusion.

2. Safety concerns

Table 3. Complications, adverse events, re-admissions to hospital (with 30 days post-operatively), and reoperations.

	Group A	Group B
Acute perioperative complications	n	n
Serious Adverse Events (SAE)	Below % will represent % of SAE/MAE/Cause of reop in group A not % of total N	Below % will represent % of SAE in group B not % of total N
Cardiovascular event	n (%)	n (%)
Pulmonary embolus	n (%)	n (%)
Deep venous thrombosis in leg	n (%)	n (%)
Subcutaneus neck haematoma	n (%)	n (%)
Systemic infection	n (%)	n (%)
Postoperative hemi- or tetraplegia	n (%)	n (%)
Persistent dysphonia at 6 months	n (%)	n (%)
Persistent dysphagia at 6 months	n (%)	n (%)
Death	n (%)	n (%)
Other	n (%)	n (%)
Minor Adverse Events (MAE)		
Wound infection	n (%)	n (%)
Motor deficit (new)	n (%)	n (%)
Persistent symptoms	n (%)	n (%)
Dyspnea (return to hospital)	n (%)	n (%)
Re-admissions to hospital (< 30 days)	n (%)	n (%)
Cause of reoperation		
Impaction of implant	n (%)	n (%)
Dislocation of implant	n (%)	n (%)
Foraminal re-stenosis	n (%)	n (%)
Wound infection	n (%)	n (%)
Wound opening	n (%)	n (%)
Other cause	n (%)	n (%)

Imbalance between the two groups in the crude incidence of safety concerns?

YES / NO

- If NO, our initial interpretation on efficacy (previous page) stands as is.
- If YES => We will add the following notion about the imbalance (excess in harms) to our interpretation:

“However, there was a noteworthy imbalance in the incidence of safety concerns in the two treatment strategies (higher/lower rate in Group A) and this should be considered when interpreting the trial findings.”

3. Unblinding

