After consideration of the major downsides of the two treatment groups, we have now reached a consensus on our blinded assessment on efficacy.

Our statistician will now unblind the treatment group assignment (break the randomization code):

Group A = Inpatient care / Outpatient care [incorrect option to be removed]

Group B = Inpatient care / Outpatient care [incorrect option to be removed]

Given the above noted, the FACADE data is shown in **Table 1** (with n-values for Groups to be added) and in Scenario 1 (**Figure 2**) or Scenario 2 (**Figure 3**). [incorrect option to be removed]

Table 2. Primary outcome at the primary outcome assessment time point (6 months).

	Group A	Group B	Difference (95% CI)
	Mean \pm SE	Mean \pm SE	
Primary efficacy outcome			
Neck Disability Index (Scale: 0 to 100)	?? \pm ??	?? \pm ??	?? \pm ??
*Means and standard errors are derived from a general linear repeated measures model analysis.			
Abbreviations: CI: Confidence Interval; SE: Standard Error			

Figure 2 or Figure 3

4. Unblinded interpretation on efficacy and clinical relevance

Accordingly, our interpretation of the FACADE trial is as follows:

[incorrect options to be removed]

(1) Inpatient care is superior to outpatient care after anterior cervical decompression and fusion. However, be it noted that we did not set a superiority hypothesis in the study protocol.

OR

(2) Inpatient care is non-inferior to outpatient care after anterior cervical decompression and fusion.

OR

(3) Inpatient care is inferior to outpatient care after anterior cervical decompression and fusion.

OR

(4) Our results are inconclusive regarding the non-inferiority of the two groups after anterior cervical decompression and fusion.

In addition to the primary conclusion above, the following notion regarding downsides of the two treatments will / will not be added [incorrect option to be removed] based on our assessment of the need for safety concerns (Section 2):

“However, there was a noteworthy imbalance in the safety of the two treatment strategies (higher/lower [incorrect option to be removed] rate in Outpatient care) and this should be considered when interpreting the trial findings.”

5. Final interpretation

Our final interpretation of the FACADE trial stands as follows:

[Copy & paste the correct interpretation]

Place: ZOOM-/Teams-meeting
Time: [Insert date here]

[name]

[name]

[name], trial statistician

Also present at the meeting (as external observers):

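### Table 3 prints shares of each arm's own events and shows no overall SAE row, so it does not display the SAE incidence on which the pre-set safety caveat depends, and the decision form does not carry the >10% rule

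*SAP*

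**What the plan says.** The rule stands in the SAP's blinded data interpretation plan, item 2 (safety concerns), before the flow chart. The committee states that "we commit to assessing the overall rate (incidence) of safety concerns before final interpretation is made as follows", and the rule follows: "If we detect > 10% difference in the overall incidence of serious adverse events between the two group (treatment strategies"), a set sentence on a noteworthy imbalance is added to the conclusion. The same item limits its reach: "the analysis on the downsides of the two treatments will not change our assessment on efficacy".

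Three later places apply the rule:

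- Flow chart, step 2, asks "Incidence of safety concerns: Imbalance", with a NO and a YES branch.
- Section 2 (Safety concerns), below Table 3, asks YES or NO on "Imbalance between the two groups in the crude incidence of safety concerns".
- Section 4 (Unblinded interpretation) adds or omits the sentence "based on our assessment of the need for safety concerns (Section 2").

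Table 3 is the display supplied for the decision. In its SAE heading row, the Group A cell reads "Below % will represent % of SAE/MAE/Cause of reop in group A not % of total N" and the Group B cell reads "Below % will represent % of SAE in group B not % of total N". The rows below are individual event types, each as n (%). They cover SAEs, minor adverse events, re-admissions and causes of reoperation.

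**The concern.** An incidence needs the patients at risk as its denominator. Table 3 expressly excludes that denominator, yet the question directly beneath it is about incidence. A share of an arm's own events describes the mix of events within that arm and says nothing about how often they occurred. Two arms with very different SAE rates can print identical percentages, and the arm with fewer events can print the larger one.

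The SAE heading row holds the note on the percentage base and no number. The shell therefore shows neither total SAEs nor patients with at least one SAE. The two notes also differ: for Group B, no base is given for the minor-event and reoperation rows.

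The form that the committee completes carries neither the SAE restriction nor the threshold. The set sentence is the plan's pre-specified way of bringing harms into the conclusion, and the document exists to fix interpretation before unblinding. The rule should therefore be visible where the answer is given, beside the quantity it uses.

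**Working it through.** **Inputs.** 104 patients randomised 1:1 (SAP, Trial design and oversight). An exact split, 52 per arm, is assumed. The threshold is >10% in overall SAE incidence (interpretation plan, item 2). It is a chosen rule without a derivation, so there is no figure to reproduce. All event counts below are illustrations.

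**1. What the threshold means in patients.** Read as percentage points, 10% of 52 is 5.2, so the gap must be at least 6 patients: 5/52 = 9.6% (not met), 6/52 = 11.5% (met).

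**2. Printed percentage against incidence.** Printed % = events in the row / all SAEs in that arm. Incidence = patients with an SAE / patients randomised. Take one SAE per patient, Group A with 2 SAEs (1 haematoma, 1 other) and Group B with 8 (4 and 4).

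| | Group A | Group B |
|---|---|---|
| Printed, haematoma | 1/2 = 50% | 4/8 = 50% |
| Printed, other | 1/2 = 50% | 4/8 = 50% |
| Overall SAE incidence | 2/52 = 3.8% | 8/52 = 15.4% |

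The difference is 6/52 = 11.5 points, so the caveat is required, yet the printed percentages are identical.

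The order can also reverse. One haematoma among 1 SAE prints 100%, and 3 among 6 SAEs print 50%. The haematoma incidences are 1/52 = 1.9% and 3/52 = 5.8%.

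**3. Whether the counts rescue the decision.** Adding the n column gives events. Suppose one arm has 6 SAEs in 4 patients and the other has none. By events the gap is 6/52 = 11.5 points (caveat); by patients it is 4/52 = 7.7 points (no caveat). The text does not say which is counted, and the Table 3 shell does not show the number of patients affected.

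**4. The unit of the 10%.** With 2 versus 3 patients with an SAE, the absolute gap is 3/52 - 2/52 = 1.9 points (no caveat), while the relative gap is (3 - 2)/2 = 50% (caveat). The text does not state which is meant.

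**5. The rule traced through the document.**

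| Place | Event set | Threshold |
|---|---|---|
| Item 2, text | SAEs | >10%, unit not stated |
| Flow chart, step 2 | safety concerns | none |
| Section 2, form | safety concerns | none |
| Section 4 | refers to Section 2 | none |

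Section 4 points to Section 2, which is the place without the threshold. None of the last three cites the text of item 2.

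**The case against.** The strongest reply concerns the trigger. A reader might infer from step 5 that the SAP holds two rival rules: SAEs with a threshold, and any safety event without one. The document does not support that. The words "we commit to assessing the overall rate (incidence) of safety concerns before final interpretation is made as follows" lead straight into the SAE rule, so the text itself defines safety concerns operationally as SAE incidence with a threshold. The form reuses the same caveat sentence, and the flow chart is presented as the order of steps. The natural reading is that the form fails to carry the rule forward.

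For the same reason, a reader should not infer that the caveat would often fire by chance. That needs cut-offs the document never states. Under the written rule in percentage points, with 52 per arm and equal true SAE rates of 5% or 10% (assumed), an exact binomial calculation gives 1.4% and 7.1%.

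On the table, the percentage base is openly labelled, counts are printed in every row, and the shell is unfilled. The statistician must know each arm's SAE total to compute the shares, so a total may yet appear. The differing notes look like a drafting slip. All of this is fair, and it means the table is not wrong about what it prints. It does not answer the central point: the planned percentages cannot inform the question beneath them, and event counts do not give patients affected.

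The stakes are also modest: one sentence, in minutes that go to an independent scientist before submission.

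**Conclusion.** The point holds as a mismatch between the display and the decision. Table 3 as specified does not show overall SAE incidence, and the form does not carry the rule that uses it. At an assumed 52 per arm, identical printed percentages can accompany an 11.5-point difference that requires the caveat. Counting events or patients can change the answer (11.5 versus 7.7 points), as can reading the 10% as absolute or relative (1.9 points versus 50%). These examples show what is possible; they do not predict the trial's results.

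The consequence is limited to the safety table and the pre-set safety sentence. A reader might infer that the non-inferiority conclusion is at risk, but the SAP separates the two explicitly. The change is worth making before the blinded meeting, because it removes discretion that the document was written to remove.

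**What to change.** - In Table 3, report each row as patients with at least one such event over patients randomised, with one identical note for both columns and N shown per group.
- Add an overall row for patients with at least one SAE.
- Repeat the SAE threshold of item 2 in flow chart step 2 and in the Section 2 form, or cite it there. State that it counts patients and give its unit; percentage points is the most natural reading.
- Settle these before the blinded meeting.

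The cost is wording and table-shell work on data already collected. The downside is that within-category shares are no longer printed, though they can be read from the counts.
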